20.1 ACCELERATED / BLAST-PHASE COHORT

Primary endpoint: The primary endpoint of this study is best overall response, defined as partial response or better (CR+PR+Cri), and will be defined as the best response within 6 cyclesof combination therapy. All patients meeting the eligibility criteria who have signed a consent form and have begun treatment will be evaluable for response. Any evaluable patient not meeting the definition for response will be deemed as having a non-response.

Design: The largest overall response rate where the proposed combination treatment regimen would be considered ineffective in this patient population is 5%, and the smallest response rate that would warrant subsequent studies with the proposed regimen is 25%. This is based on retrospective analysis applying the 2013 IWG Response Criteria to patients treated with ruxolitinib¹. A Simon's two-stage minimax design will be employed to test the null hypothesis that the true overall response rate in this patient population is at most 5%.

Decision Rule: Enter 13 patients into the study. If 0 responses are observed in the first 13 patients (Stage 1), we may consider this regimen ineffective in the patient population and the trial will close due to a lack of efficacy. If 1 or more responses are observed in the first 13 evaluable patients, we will proceed to Stage 2 and enroll an additional 7 patients onto the study for a total of 20 patients. After completion of both stages, if 3 or more responses out of the 20 patients are observed, the combination therapy will be considered promising for further investigation.

20.1.2 POWER AND SIGNIFICANCE LEVEL / PRECISION

Assuming that the number of overall response is binomially distributed, the significance level is <0.10 and the probability of declaring that this regimen warrants further studies (i.e., statistical power) under various response proportions can be tabulated as a function of the true response proportion as shown in the following table.

Table 6. Statistical Power

MPN

Accelerated / Blast-Phase MPN								
If the true response rate is	0.05	0.10	0.15	0.20	0.25			
Then the probability of early termination of the study is	0.51	0.25	0.12	0.05	0.02			
Then the probability of declaring that the regimen warrants further studies is	0.07	0.32	0.59	0.79	0.90			

20.2 CHRONIC MPN PHASE

Primary endpoint: The primary endpoint of this study is best overall response, defined as clinical improvement or better (CI+PR+CR) according to IWG-ELN criteria, and will be defined as the best response within 6 cycles of combination therapy. All patients meeting the eligibility criteria who have signed a consent form and have begun treatment will be evaluable for response. Any evaluable patient not meeting the definition for response will be deemed as having a non-response.

in Patients with Accelerated/Blast-phase Myeloproliferative Neoplasm or Chronicphase Myelofibrosis with an IDH2 Mutation

(Myeloproliferative Neoplasms Research Consortium [MPN-RC] 119)

Design: Based on a Gehan design, observation of at least 1 response out of 9 evaluable patients would indicate activity in this cohort. This design has 90% power if the true response rate is 25%.

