6.2.1 CLINICAL EXPERIENCE IN MYELOFIBROSIS WITH RUXOLITINIB

MPN-RC

A Phase II Open-label Study of Combined Ruxolitinib and Enasidenib Sinai Sinai in Patients with Accelerated/Blast-phase Myeloproliferative Neoplasm or Chronic-

phase Myelofibrosis with an IDH2 Mutation

(Myeloproliferative Neoplasms Research Consortium [MPN-RC] 119)

Ruxolitinib has been shown to produce durable clinical benefits in terms of spleen volume reduction and improvement in constitutional symptoms with an acceptable toxicity profile^{27,28}. Based on the results of two Phase III studies (COMFORT-I, COMFORT-II)^{27,28} showing improvement in spleen size, symptom control and improvement in quality of life, ruxolitinib was approved for use in patients with intermediate or high-risk myelofibrosis by the FDA. There is also evidence of a benefit in overall survival (OS) in patients treated with ruxolitinib. An OS advantage (HR=0.58; 95% CI, 0.39-0.85, p=0.005) in treated patients compared to historical controls has been reported²⁹. In addition, an analysis of the COMFORT-I study confirmed that patients treated with ruxolitinib had an OS advantage compared with placebo (HR=0.58,95%CI, 0.36-0.95, p-0.03) with a median of 102 weeks of followup³⁰. Follow-up analysis of the COMFORT-II trial has also demonstrated an OS advantage for patients treated with ruxolitinib³¹.

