10. TREATMENT DOSAGE AND ADMINISTRATION

Patients who are on ruxolitinib will continue their current dose. Patients who are not on ruxolitinib will receive ruxolitinib per Table 1 dosing based on platelet count (modified package insert dosing). Enasidenib will be given at 100 mg daily on enrollment for patients with accelerated and blast phase myelofibrosis regardless of platelet count (this will be deemed Cycle 1). Patients with chronic phase myelofibrosis will receive Enasidenib at starting dose of 50 mg daily for cycle 1. The dose of Enasidenib will be increased to 100 mg for cycle 2 if the platelet count stays above 50,000 at the end of cycle 1 (Table 3a) and no other therapy emergent SAE of grade \geq 2 developed (except grade 2 hyperbilirubinemia that is acceptable for dose escalation).

Ruxolitinib and enasidenib will be given orally in an outpatient setting unless the patient is being seen inpatient for another reason. Ruxolitinib and enasidenib will be given orally in 28-day cycles.

Patients should fast 2 hours before and 1-hour post enasidenib. Ruxolitinib may be administered independent of fasting and may be given with enasidenib. All protocol mandated visits will be performed at one of the participating institutions. Patients will return to the treating institution at a minimum of weekly during Cycles 1 and 2, every 4 weeks for Cycles 3 and beyond. Additional clinic visits will be mandated according to the patient clinical condition and at the discretion of the treating provider. Patients will have an end of study visit for a safety follow-up at 30 days after their last dose of therapy.

The dosages of ruxolitinib and/or enasidenib can be reduced, based on assessment of adverse events, if any occur, as described below in Section 10.1. Missed or vomited doses of ruxolitinib or enasidenib will not be made up.

Twenty-eight days is considered one cycle of therapy. Attempts will be made to provide an adequate treatment period with the combination of at least 6 cycles, unless significant toxicity is observed, to account for delayed time to response observed with biologic agents. Responders will continue therapy indefinitely unless progression of disease occurs, toxicity warranting discontinuation of therapy is

A Phase II Open-label Study of Combined Ruxolitinib and Enasidenib Sinai in Patients with Accelerated/Blast-phase Myeloproliferative Neoplasm or Chronic-

phase Myelofibrosis with an IDH2 Mutation

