20. STATISTICAL CONSIDERATIONS

STUDY DESIGN/STUDY ENDPOINTS

This is a Phase II design to evaluate the efficacy of ruxolitinib and enasidenib combination therapy for accelerated or blast-phase MPN patients with IDH2 mutations. The study will also include a descriptive cohort of up to 9 evaluable patients with chronic phase MPN and will utilize a Gehan design in this cohort. This study will be the first time ruxolitinib and enasidenib will be used in combination for this patient population. Therefore, the safety of the combination will be confirmed in the first six patients

MPN-RC

in Patients with Accelerated/Blast-phase Myeloproliferative Neoplasm or Chronicphase Myelofibrosis with an IDH2 Mutation

(Myeloproliferative Neoplasms Research Consortium [MPN-RC] 119)

who are enrolled in the study. If no more than one patient out of the initial six has a treatment-related Grade 3 or higher adverse event attributable to the study drugs, the combination therapy will be considered safe. If more than one patient out of the initial six has a limiting toxicity the trial will be suspended, and the safety data will be further reviewed.

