	<unl; <2%="" and<="" cells‡="" immature="" myeloid="" td=""></unl;>
	Clinical: Resolution of disease symptoms; spleen and liver not palpable; no evidence of EMH or
	Bone marrow:* Age-adjusted normocellularity; <5% blasts; ≤grade 1 MF†, and peripheral blood: Hemoglobin ≥85 but <100 g/L and <unl; 109/L and <unl; 10<sup="" <100="" but="" count="" platelet="" ×="" ≥50,="">9/L and <unl; <2%="" immature="" myeloid<="" td=""></unl;></unl;></unl;>
	cells‡ and
	Clinical: Resolution of disease symptoms; spleen and liver not palpable; no evidence of EMH
Clinical improvement (CI)	The achievement of anemia, spleen or symptoms response without progressive disease or increase in severity of anemia, thrombocytopenia, or neutropenia§
Anemia response	Transfusion-independent patients: a \geq 20 g/L increase in hemoglobin levell
	Transfusion-dependent patients: becoming transfusion-independent
Spleen response#	A baseline splenomegaly that is palpable at 5-10 cm, below the LCM, becomes not palpable** or
	A baseline splenomegaly that is palpable at >10 cm, below the LCM, decreases by \geq 50%**
	A baseline splenomegaly that is palpable at <5 cm, below the LCM, is not eligible for spleen response
	A spleen response requires confirmation by MRI or computed tomography showing ≥35% spleen volume reduction
Symptoms response	A ≥50% reduction in the MPN-SAF TSS11
Progressive disease‡‡	Appearance of a new splenomegaly that is palpable at least 5 cm below the LCM or
	A \ge 100% increase in palpable distance, below LCM, for baseline splenomegaly of 5-10 cm or
	A 50% increase in palpable distance, below LCM, for baseline splenomegaly of >10 cm or
	Leukemic transformation confirmed by a bone marrow blast count of ≥20% or
	A peripheral blood blast content of \geq 20% associated with an absolute blast count of \geq 1 × 10(9)/L that lasts for at least 2 weeks
Stable disease	Belonging to none of the above listed response categories
Relapse	No longer meeting criteria for at least CI after achieving CR, PR, or CI, or
	Loss of anemia response persisting for at least 1 month or
	Loss of spleen response persisting for at least 1 month
	Recommendations for assessing treatment-induced cytogenetic and molecular changes
Cytogenetic remission	At least 10 metaphases must be analyzed for cytogenetic response evaluation and
	requires confirmation by repeat testing within 6 months window
	CR: eradication of a preexisting abnormality

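### One response in nine chronic-phase patients is read as activity, but with no uninteresting rate stated the rule can only screen out inactivity

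*Combined protocol and SAP*

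**What the plan says.** Section 20 describes a "descriptive cohort of up to 9 evaluable patients with chronic phase MPN and will utilize a Gehan design". Section 20.2 then gives the rule, "observation of at least 1 response out of 9 evaluable patients would indicate activity in this cohort", and its only operating characteristic: "This design has 90% power if the true response rate is 25" (per cent). No uninteresting response rate, significance level or pass probability at a low rate is given for this cohort.

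Response in 20.2 is "defined as clinical improvement or better (CI+PR+CR) according to IWG-ELN criteria", within 6 cycles. The table in Appendix B, on which Appendix A relies, defines clinical improvement as "The achievement of anemia, spleen or symptoms response without progressive disease or increase in severity of anemia, thrombocytopenia, or neutropenia".

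On ruxolitinib, Section 6.2.1 credits the drug itself with "durable clinical benefits in terms of spleen volume reduction and improvement in constitutional symptoms". Section 8.1 permits prior ruxolitinib but does not require it. Section 10 adds: "Patients who are not on ruxolitinib will receive ruxolitinib per Table 1 dosing". Section 10.3 allows ruxolitinib to be escalated, among other reasons for suboptimal response. It cites the dose levels of Table 2a (accelerated/blast phase), but Table 2b for chronic phase also carries a +1 level, so I read escalation as open to this cohort.

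For comparison, Section 20.1 fixes both benchmark rates for the accelerated/blast-phase cohort: "considered ineffective in this patient population is 5%, and the smallest response rate that would warrant subsequent studies with the proposed regimen is 25" (per cent). Table 6 tabulates that design's pass probabilities.

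**The concern.** A threshold of one response is the lowest possible bar. It becomes evidence of activity only if one response would be surprising under an inactive regimen, and the plan never says what rate it would regard as inactive here. The other cohort treats similar evidence more cautiously: one response among 13 only opens Stage 2, and a favourable conclusion needs 3 of 20. In chronic phase, one response among fewer patients is itself the conclusion.

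The endpoint adds to the difficulty. It counts clinical improvement, and two of the three routes to it (spleen and symptoms) are effects the protocol already attributes to ruxolitinib. A report that followed 20.2 as written could claim activity on one such response, next to an interval whose lower limit is close to zero.

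**Working it through.** **Inputs.** Rule: at least 1 response, n = 9 (20.2). Design rate 25%, stated power 90% (20.2). Ineffective rate 5%, for accelerated/blast phase only, on CR+PR+CRi (20.1). Exact two-sided 95% interval (22.1). Assumed for the chronic cohort: an uninteresting rate of 5–10%, and a range of 15–30% for the clinical-improvement-or-better rate on ruxolitinib alone. The documents give neither figure.

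**1. The plan's own figure.** P(at least 1 of n) = 1 − (1 − p)^n.
- n = 8, p = 0.25: 1 − 0.75^8 = 0.8999, just under 90%.
- n = 9, p = 0.25: 1 − 0.75^9 = 1 − 0.0751 = 0.9249.

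Nine is the smallest n that reaches 90%. The stated 90% is the nominal target, and the exact value exceeds it.

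**2. Pass probability at other true rates (n = 9).**

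| True rate | P(at least 1 of 9) |
|---|---|
| 5% | 1 − 0.95^9 = 0.370 |
| 10% | 1 − 0.90^9 = 0.613 |
| 15% | 1 − 0.85^9 = 0.768 |
| 20% | 1 − 0.80^9 = 0.866 |
| 25% | 0.925 |
| 30% | 1 − 0.70^9 = 0.960 |

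**3. What each result can say.** The exact (Clopper-Pearson) 95% interval for 1/9 is 0.3% to 48.2%, so one response excludes almost no low rate. For 0/9, the probability at a true 25% is 0.75^9 = 0.075, and it is smaller at any higher rate. That is a usable signal of inactivity, though not an exclusion: the exact two-sided 95% interval for 0/9 is 0% to 33.6%.

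**4. The accelerated/blast-phase design for comparison.** With Stage 1 of 13 (continue if at least 1 response) and success at 3 or more of 20, the success probability is the sum over x = 1 to 13 of P(X1 = x) × P(X2 ≥ 3 − x), with X1 ~ Bin(13, p) and X2 ~ Bin(7, p). This gives 0.074 at 5% and 0.317 at 10%, matching the 0.07 and 0.32 in Table 6. The Stage 1 gate alone passes with probability 1 − 0.51 = 0.49 at 5% and 1 − 0.25 = 0.75 at 10% (Table 6). A rule of one or more responses thus behaves as a gate in both cohorts, but only in chronic phase is passing it called activity.

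**5. If ruxolitinib alone produced the responses.** At an assumed ruxolitinib-alone rate of 15% to 30%, the rule passes with probability 0.77 to 0.96 with no contribution from enasidenib.

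**6. Would a higher threshold help?** Requiring at least 2 of 9 gives 0.071 at 5% and 0.225 at 10%, but only 0.700 at 25%. Nine patients cannot support both a low false-pass rate and the stated power, which favours descriptive reporting over a new cut-off.

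**The case against.** The best defence is that little depends on this rule. Sections 11.4, 14.0, 20 and 21 call the cohort descriptive. Section 13.2 lists its response rate as a secondary endpoint, although 20.2 uses the word primary for it. Sections 22.1 and 22.2 already plan an exact 95% interval, and 20.2 attaches no stopping, expansion or further-study decision to 1/9. All of this stands, and it limits the consequence. It does not remove the sentence that turns one response into a finding; a descriptive cohort has no need of that sentence.

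The attribution argument also has limits. Chronic-phase patients must be previously treated with persistent or progressive disease. Those already on ruxolitinib need at least 3 months on the drug and at least one month at a stable dose, so a new response on an unchanged dose is harder to credit to ruxolitinib. Appendix B requires benefit lasting at least 12 weeks and imaging confirmation of a spleen response. The anemia route is not one the protocol credits to ruxolitinib: Section 18.3 lists anemia among its toxicities, at 72% to 96%. The point therefore applies mainly to patients who start or escalate ruxolitinib on study, and the documents do not say how many there will be.

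Three stronger readings are tempting and are not supported:
- That the 90% power is wrong. It is a conservative nominal figure for the smallest adequate n.
- That the rule will almost always report activity even if enasidenib adds nothing. It passes 37% of the time at 5% and 61% at 10%. A figure near 90% needs a background rate of about 20% or more, which the documents do not provide.
- That one clinical improvement says nothing about the combination. The objective in 7.2 concerns the combination, and a response in a patient starting both drugs is a response to that regimen. What it cannot do is separate enasidenib's part.

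**Conclusion.** The concern holds in a limited form. The rule supports a statement about inactivity after 0/9; it does not support a statement of activity after 1/9. Its chance of passing is 0.37 to 0.61 if the uninteresting rate is 5–10%, an assumption for this cohort. The plan's own 5% is a guide only, since it was set for accelerated/blast-phase disease and an endpoint that excludes clinical improvement. At 20% the chance is 0.87. The attribution problem is qualitative; the 0.77 to 0.96 range depends on an assumed ruxolitinib-alone rate of 15–30%. The primary, accelerated/blast-phase conclusion is untouched. The point is still worth correcting, because it changes what may be claimed for the chronic-phase cohort and costs little.

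**What to change.** 1. In 20.2, replace the activity statement with wording to this effect: no responses in 9 makes a true rate of 25% or more unlikely (probability at most 7.5%); any other result is reported descriptively as a count with the exact 95% confidence interval planned in 22.1, with no claim of activity.
2. Add the pass probabilities of the one-response threshold at true rates of 5%, 10% and 20% (0.37, 0.61, 0.87). The power sentence may stay; at most, word it as at least 90% (exact 92.5%).
3. Tabulate clinical improvement separately for patients who start or escalate ruxolitinib on study and for those on stable ruxolitinib. Escalation is a post-baseline event, so the split is descriptive and not a comparison.

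**Cost.** Wording and one table split. Prior treatment and concomitant medication are recorded under 14.1, and a drug dosage form is listed in Table 7, so no patients, visits or endpoints are added. The price is a weaker chronic-phase claim.

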21. SAMPLE SIZE AND ACCRUAL

The maximum sample size in the Phase II (accelerated/blast-phase) is 20 evaluable patients. Allowing for enrollment of up to 2 additional patients as replacements for unevaluable patients (ineligibility, cancellation, major treatment violation, or other reasons), this study will enroll a maximum of 22 patients in the Phase II AP/BP cohort. The maximum sample size in the chronic phase MPN is 9 evaluable patients. Allowing for enrollment of up to 1 additional patient as replacement for unevaluable patients, this study will enroll a maximum of 10 patients in the descriptive chronic phase MPN cohort. Therefore, a maximum total of 32 (22 + 10) patients will be enrolled in the trial.

The anticipated accrual rate is approximately 2-3 patients per month. Therefore, the accrual period for this study is expected to be 15 months. The primary analysis can begin approximately 21 months after the trial begins, i.e., as soon as the last patient has been observed for 6 cycles.

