11.4 PATIENT ACCRUAL

MPN-RC

Subjects are considered evaluable as long as they have signed informed consent, are eligible for participation and started study treatment. The maximum sample size in the Phase II (accelerated/blast-phase) is 20 evaluable patients. Allowing for enrollment of up to 2 additional patients to account for ineligibility, cancellation, major treatment violation, or other reasons, this study will enroll a maximum of 22 patients in the Phase II AP/BP cohort. The maximum sample size in the chronic phase MPN is 9 evaluable patients. Allowing for enrollment of up to 1 additional patient, this study will enroll a maximum of 10 patients in the descriptive chronic phase MPN cohort. Therefore, a maximum total of 32 (22 + 10) patients will be enrolled in the trial.

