22. DATA ANALYSIS PLANS

22.1 PRIMARY ENDPOINT

Overall response rate (ORR): The overall response rate will be estimated by the number of patients that attain a response (defined above per cohort) by 6 cycles of combination therapy divided by the total number of treated eligible patients. A two-sided 95% confidence interval for the true overall response rate will be calculated according the exact binomial method.

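### Section 21 lets a treated, eligible accelerated/blast-phase patient be called unevaluable and replaced, which Sections 11.4, 20.1 and 22.1 do not allow

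*Combined protocol and SAP*

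**What the plan says.** Four parts of the combined protocol and SAP bear on who counts in the accelerated/blast-phase cohort.

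- **Section 20.1** sets the evaluability rule: "All patients meeting the eligibility criteria who have signed a consent form and have begun treatment will be evaluable for response". It then sets the default outcome: "Any evaluable patient not meeting the definition for response will be deemed as having a non-response". The Stage 1 decision uses the same term: "If 1 or more responses are observed in the first 13 evaluable patients", the trial goes on to 7 more patients, for a total of 20, and 3 or more responses make the regimen promising.
- **Section 11.4** gives the same rule: "Subjects are considered evaluable as long as they have signed informed consent, are eligible for participation and started study treatment". Later in the same paragraph it allows up to 2 extra patients "to account for ineligibility, cancellation, major treatment violation, or other reasons".
- **Section 22.1** computes the response rate as responders "divided by the total number of treated eligible patients".
- **Section 21** describes the extra enrolment as follows: "Allowing for enrollment of up to 2 additional patients as replacements for unevaluable patients (ineligibility, cancellation, major treatment violation, or other reasons". The ceiling is 20 evaluable and 22 enrolled.

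Section 20.1.2 states that "the significance level is <0.10 and the probability of declaring that this regimen warrants further studies" is shown in Table 6. That table gives 0.07 at a true response rate of 5% and 0.90 at 25%.

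**The concern.** Under Sections 11.4, 20.1 and 22.1, an eligible patient who has started treatment cannot be unevaluable. Ineligibility fits that rule, and so does cancellation if it means never starting. The other two grounds in Section 21 do not fit so easily. A major treatment violation normally happens to someone already on treatment, and the final catch-all has no boundary. No section defines the violation or confines either ground to untreated patients.

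The documents therefore give two answers for a treated eligible patient with a major violation: count as a non-responder, or set aside and replace. Either decision boundary can turn on one patient. The trial is open-label with a single arm, so the classification could be made after the patient's course is known. If such patients tend to be non-responders, replacing them raises both the observed response rate and the chance of a positive decision.

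**Working it through.** **1. The passages side by side, for a treated eligible patient with a major violation**

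| Section | Status of this patient |
|---|---|
| 11.4, definition | Evaluable |
| 20.1 | Evaluable; non-responder unless response criteria are met |
| 22.1 | In the denominator |
| 11.4, allowance | One of the reasons for enrolling an extra patient; not called unevaluable |
| 21 | Unevaluable; replaced |

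**2. Reproduce Table 6**

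Inputs from Section 20.1: null rate 5%, target rate 25%, Stage 1 of 13 patients with a stop at 0 responses, total of 20, success at 3 or more. With X1 ~ Bin(13, p) and X2 ~ Bin(7, p):

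P(promising) = P(X1=1)·P(X2≥2) + P(X1=2)·P(X2≥1) + P(X1≥3)

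- p = 0.05: 0.3512 × 0.0444 + 0.1109 × 0.3017 + 0.0245 = 0.0156 + 0.0335 + 0.0245 = **0.0736** (Table 6: 0.07)
- p = 0.25: 0.1029 × 0.5551 + 0.2059 × 0.8665 + 0.6674 = 0.0571 + 0.1784 + 0.6674 = **0.903** (Table 6: 0.90)

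The early-termination probabilities, 0.95^13 = 0.513 and 0.75^13 = 0.024, also match the printed 0.51 and 0.02.

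**3. Treated non-responders dropped and replaced**

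Assumption (worst case): every replaced patient is a non-responder, and the cut-off of 3 is unchanged. Dropping a non-responder and treating one more patient gives the same chance of a positive decision as counting responders among one more treated patient. The same two-stage formula applies, with Stage 1 and total sizes changed:

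| Replacements | Equivalent Stage 1 / total | False-positive rate at 5% |
|---|---|---|
| None | 13 / 20 | 0.0736 |
| One, in Stage 2 | 13 / 21 | 0.0819 |
| One, in Stage 1 | 14 / 21 | 0.0831 |
| Two, both in Stage 2 | 13 / 22 | 0.0905 |
| Two, one in each stage | 14 / 22 | 0.0920 |
| Two, both in Stage 1 | 15 / 22 | 0.0931 |

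All stay below 0.10.

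**4. Treated patients kept and the replacements also counted**

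The denominator becomes 21 or 22, for which no cut-off is stated. Keeping Stage 1 at 13:

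| Total | Cut-off | False-positive rate at 5% | Power at 25% |
|---|---|---|---|
| 21 | 3 | 0.0819 | 0.918 |
| 22 | 3 | 0.0905 | 0.930 |
| 21 | 4 | 0.0187 | 0.806 |
| 22 | 4 | 0.0219 | 0.834 |

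The cut-off of 4 is not in the documents. It is shown only because 3 of 20 does not say what applies at 21 or 22.

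**5. Effect on the reported rate (exact binomial 95% interval, as in Section 22.1)**

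- 3/20 = 15.0% (3.2% to 37.9%)
- 3/21 = 14.3% (3.0% to 36.3%)
- 3/22 = 13.6% (2.9% to 34.9%)

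**The case against.** The strongest reply is that the governing rule is clear and repeated. The study summary and Sections 11.4 and 20.1 all define evaluability by eligibility, consent and starting treatment, and Section 22.1 fixes the denominator. The disputed words are a parenthesis in a paragraph about the enrolment ceiling, and specific analysis text would ordinarily prevail over it. The contradiction also rests on an inference. The violation is undefined, and some kinds, such as never starting the combination, would fit the evaluability rule. If every treated eligible patient is evaluable, the ceiling of 20 evaluable patients is reached at the twentieth, so a denominator of 21 or 22 should not arise. Finally, even the worst case keeps the false-positive rate inside the stated limit.

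Much of this stands. The analysis rule is sound, the design figures reproduce, and the effect is small. The 21-or-22 case arises only if Section 21's replacement clause is followed while treated patients also stay in the denominator. The conflict remains, however. No section restricts the two grounds to untreated patients or says which text prevails. A site or study team following Section 21 as written could replace a treated patient whom Section 20.1 counts as a non-responder.

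**Conclusion.** The concern holds, and it is minor. Section 21, read literally, allows a treated eligible patient to be set aside after treatment has begun, which Sections 11.4, 20.1 and 22.1 do not allow. The fault lies in the text, not in the arithmetic or the choice of design.

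In the assumed worst case, with both extra places used for treated non-responders, the false-positive rate goes from 0.074 to at most 0.093, and three responders are reported as 15.0% instead of 13.6%. These figures depend on replacements actually occurring; they are not the design's expected error rate. If the decision set is the first 20 eligible treated patients, the rate stays at 0.074 and power at 0.90.

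**What to change.** In Section 21, and in the matching phrase of Section 11.4:

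- Limit replacement to patients who never start treatment or who are confirmed ineligible from data collected before treatment.
- Delete the last two of the four listed grounds, the treatment violation and the catch-all.
- State that the first 13 and the first 20 eligible treated patients, in order of treatment start, form the Stage 1 and final decision sets.

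This follows the rule already in Sections 11.4, 20.1 and 22.1. It takes two or three sentences and needs no extra patients or analyses. The observed response rate may be slightly lower, because treated patients with violations stay in the denominator.
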